3.3.8 Investigational Product Administration

Investigational product single dose is 0.8 mL in volume and administered by IM injection into the deltoid with a pre-filled syringe attached to 25 gauge 1" (or 1.5") needle, using universal precautions and sterile technique in accordance with General Best Practice Guidelines for Immunization: Best Practices Guidance of the Advisory Committee on Immunization Practices (ACIP) (27) per Table 1. Injections will be administered by a staff member delegated by the investigator.

Table 1Needle Length of Intramuscular Injections for Children (by Age) and Adults Aged ≥19Years (By Sex and Weight)

Sex, Weight	Needle length	Injection Site
Men and women, <60 kg (<130 lbs)	1 inch (25 mm)	
Men and women, 60-70 kg (130-152 lbs)	1 inch (25 mm)	Deltoid muscle of arm
Men, 70-118 kg (152-260 lbs)	1 1 5 in ale a (25 29 mm)	
Women, 70-90 kg (152-200 lbs)	1-1.5 menes (25-58 mm)	
Men, >118 kg (260 lbs)	1.5 in shee (20 mm)	
Women, >90 kg (200 lbs)	1.5 inches (38 mm)	
Children, 12 to <18 years of age	5/8 ¹ -1 inch (16-25 mm)	

Source: Adapted from Table 6-2, General Best Practice Guidelines for Immunization: Best Practices Guidance of the Advisory Committee on Immunization Practices (ACIP) (27).

¹If skin is stretched tightly and subcutaneous tissues are not bunched.

Investigational product is to be administered only under the direct supervision of the investigator or a qualified subinvestigator identified on the FDA Form 1572. Under no circumstances will the investigator allow PXVX0317 vaccine to be used other than as specified in the protocol.

For further details on the IP refer to Section 5.1.

3.3.9 Acute Observation After Investigational Product Administration

The participant will be monitored by study staff for signs of an acute adverse reaction for 30 min after injection. Vital signs will be obtained 30 min to 1 hr after injection.

3.3.10 Solicited Adverse Events

Solicited AEs will be collected from IP administration until Day 8. Solicited AEs for this study are local events of pain, redness, and swelling at the injection site and systemic events of oral temperature \geq 38.0°C (\geq 100.4°F), chills, fatigue, headache, myalgia, arthralgia, and nausea (Section 7.1.2 and Section 7.1.2.1).

Participants will be trained to complete an e-diary to observe, measure, and record these solicited AEs. In the occurrence of issues with the e-diary, a paper diary (subject memory aid) may be implemented as a back up. To measure oral temperature, a digital thermometer will be provided to the participant to measure their temperature each day and record them in their e-diary. To record injection site local reactions, a ruler will be provided to the participant to measure of redness and swelling at the largest point of the reaction each day. Adolescent participants will be instructed to complete the e-diary. Parents/guardians may provide assistance to adolescents to measure and record temperature and injection site reactions.

Study staff will review the signs and symptoms recorded in the e-diary. The investigator will then assess all solicited AEs for severity (Section 7.1.7) and the action taken, and causality (Section 7.1.8). The results of the investigator's assessment will be recorded as a separate source document and will be entered on the solicited AE eCRF. Symptoms continuing beyond the solicited AE collection period will be collected and recorded on the AE eCRF.

Details on definition, evaluation, reporting periods and documentation are outlined in Section 7.

3.3.11 Unsolicited Adverse Events

Unsolicited AEs (AEs not listed in the e-diary) will be collected from Day 1 through 28 days postvaccination (Day 29) (Section 7.1.3).

Details on definition, evaluation, reporting periods and documentation are outlined in Section 7.

3.3.12 Serious Adverse Events and Adverse Events of Special Interest

Serious adverse events, AESI, and MAAEs will be collected for all participants from Day 1 through Day 183 End of Study Visit (Section 7.1.4 and Section 7.1.5).

Details on definition, evaluation, reporting periods and documentation are outlined in Section 7.

3.4 Measures Taken to Minimize/Avoid Bias

3.4.1 Treatment Assignment/Randomization

Participant eligibility will be confirmed and documented by the investigator immediately prior to randomization of each participant. Study staff will indicate on a randomization eCRF within the electronic data capture (EDC) system that they want to generate a randomization number for the participant. When they agree to proceed, a randomization number will be generated from the EDC randomization module but hidden from study staff. The EDC randomization module will match the randomization number to an IP kit available at the site
PXVX0317 Vaccine EBSI-CV-317-004, Version 5.0 20 Mar 2023

and inform the study staff of the assigned kit. Study staff will use the appropriate kit for administration to the participant.

Participants will be considered enrolled once a randomization number has been assigned within the EDC system. The study will be conducted as a double-blind study through Day 183 End of Study Visit. Neither participants, nor clinical site personnel, including the investigators, nor the sponsor will know participants' individual treatment assignments until all participants have completed their participation in the study through the Day 183 End of Study Visit and the database has been cleaned and locked.

3.4.2 Masking/Blinding Procedures

Study participants, the investigator, and study site personnel will remain blinded to all randomization assignments throughout the study. The sponsor's MM and personnel, who are in regular contact with the study site and/or involved with documentation associated with the study will remain blinded to all participant randomization assignments.

The following safeguards will be employed to reduce the risk of inadvertent unblinding:

- Use of a standardized pre-filled syringe and injection volume for all injections.
- All PXVX0317 and placebo syringes have a semitransparent barrel cover to mask any difference in appearance between placebo and PXVX0317.
- No sponsor personnel will have access to the randomization schedule. No site personnel will have access to treatment assignments. The Randomization and Trial Supply Management (RTSM) system allows for unblinding in an emergency (see Section 7.7).
- Assays will be run in a blinded manner. The assay titer results will not be delivered to the sponsor data management and analysis team until after database lock, as they are potentially unblinding.
- Should any participant or staff member become inadvertently unblinded, the investigator will promptly (within 24 hours of their awareness of the error) disclose the event to the sponsor's MM in a blinded fashion (disclosing only participant number, not treatment) so that corrective action can be initiated. The unblinding sequence of events will be documented and retained as source documents. A protocol deviation will be entered in the eCRF.

3.5 End of Study

An individual participant is considered to have completed study participation after completion of the Day 183 (-14/+7) Visit 8 and any required safety follow-up.

4 SELECTION AND WITHDRAWAL OF PARTICIPANTS

4.1 Inclusion Criteria

Participants must meet all the following criteria to be enrolled:

- 1. Able and willing to provide informed consent (and assent, as applicable) voluntarily signed by participant (and guardian, as applicable).
- 2. Males or females, 12 to <65 years of age.
- 3. Generally healthy, in the opinion of the investigator, based on medical history, physical examination, and screening laboratory assessments.
- 4. Women who are either:
 - Not of CBP: pre-menarche, surgically sterile (at least six weeks post bilateral tubal ligation, bilateral oophorectomy, or hysterectomy), or postmenopausal (defined as a history of ≥12 consecutive months without menses prior to randomization in the absence of other pathologic or physiologic causes, following cessation of exogenous sex-hormonal treatment).

or:

- ii. Meeting all the below criteria:
 - Negative serum pregnancy test at Screening Visit
 - Negative urine pregnancy test immediately prior to dosing at Day 1
 - Use one of these acceptable methods of contraception (if women of CBP) for the duration of participation:
 - Hormonal contraceptives (eg, implants, pills, patches) initiated ≥30 days prior to dosing
 - Intrauterine device inserted \geq 30 days prior to dosing
 - Double barrier type of birth control (male condom with female diaphragm, male condom with cervical cap)
 - Abstinence is acceptable only for adolescents (12 to <18 years old) who are not sexually active.

Note: See Section 3.3.7 for this study's list of acceptable method of contraception.

Note: Contraception requirements do not apply for participants in exclusively same-sex relationships and these participants should have no plans to become pregnant by any other means for the duration of the study.

4.2 Exclusion Criteria

Participants who meet **any** of the following criteria **cannot** be enrolled:

- 1. Currently pregnant, breastfeeding, or planning to become pregnant during the study.
- 2. Body mass index \geq 35 kg/m².
- 3. Positive laboratory evidence of current infection with HIV-1/HIV-2, HCV, or HBV.
- 4. History of severe allergic reaction or anaphylaxis to any component of the IP.
- 5. History of any known congenital or acquired immunodeficiency that could impact response to vaccination (eg, leukemia, lymphoma, generalized malignancy, functional or anatomic asplenia, alcoholic cirrhosis).
- 6. Prior receipt or anticipated use of systemic immunomodulatory or immunosuppressive medications from six months prior to screening through Day 22. **Note:** For systemic corticosteroid use at a dose or equivalent dose of 20 mg of prednisone daily for 14 days or more within three months of screening through Day 22 is exclusionary. The use of inhaled, intranasal, topical, ocular, or intraocular steroids is allowed.
- 7. Receipt or anticipated receipt of blood or blood-derived products from 90 days prior to screening through Day 22.
- 8. Acute disease within the last 14 days (participants with an acute mild febrile illness can be considered for a deferral of vaccination two weeks after the illness has resolved and treatment has been completed).
- 9. Clinically significant cardiac, pulmonary, rheumatologic, or other chronic disease, in the opinion of the investigator. This may include chronic illness requiring hospitalization in the last 30 days prior to screening.
- 10. Enrollment in an interventional study and/or receipt of another investigational product from 30 days prior to screening through the duration of study participation.
- 11. Receipt or anticipated receipt of any vaccine from 30 days prior to Day 1 through Day 22.
- 12. Evidence of substance abuse that, in the opinion of the investigator, could adversely impact the participant's participation or the conduct of the study.
- 13. Prior receipt of an investigational CHIKV vaccine/product.
- 14. Any other medical condition that, in the opinion of the investigator, could adversely impact the participant's participation or the conduct of the study.

4.3 Withdrawal of Participants

4.3.1 Participant Consent Withdrawal

All participants can withdraw from participation in this study at any time, for any reason, specified or unspecified, and without penalty. The investigator will ask (but cannot require) such participants to provide the reason(s) for withdrawal of consent and to undergo an Early Withdrawal Visit. An individual is considered to undergo early withdrawal if they stop study participation before Day 183 End of Study Visit.

Safety follow-up for AEs should occur for all participants. For information on safety follow-up for withdrawn participants see Section 4.3.3.

4.3.2 Investigator-Based Participant Withdrawal

The Investigator may withdraw a participant from further participation in the study, at their discretion, if medically necessary or for reasons of noncompliance. The reason for withdrawal of any participant must be clearly documented on the study source documents and the appropriate eCRF. The investigator is encouraged to consult the sponsor prior to the withdrawal of any participant, except in the event of a medical emergency.

The investigator (and/or sponsor) may withdraw a participant from the study for any of, but not limited to, the following reasons:

- Noncompliance with the protocol. If the participant is noncompliant with protocol requirements, the issue should be discussed with the participant and, if not resolved, consideration given to withdrawing the participant.
- Lost to follow-up; requires documentation of at least three unsuccessful attempts to contact participants. Lost to follow-up will be determined after the date of the participant's projected last visit.
- Other reason(s) which, in the opinion of the investigator, indicates that continued participation in the study is not in the best interest of the participant.

Safety follow-up for AEs should occur for all participants. For information on safety follow-up for withdrawn participants see Section 4.3.3.

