4.3.3 Follow-up for Withdrawn Participants

Outreach will be made to ensure that participants who are withdrawn, or who withdraw from the study, during the active observation or follow-up period will complete all safety and available assessments for the Early Withdrawal Visit as outlined in this protocol. The investigator should inform the participant that these assessments are for their own well-being and, if possible, for study purposes. Additional information regarding ongoing AEs may be provided as a follow-up report.

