4.3.4 Documentation of Withdrawal/Discontinuation

Reasons for withdrawal of individual participants from the study prior to final protocol required visit and/or final safety follow-up are to be recorded on the eCRF. The reason for withdrawal from the study will be recorded as one of the following:

- Lost to Follow-up (**Note:** Requires documentation of at least three unsuccessful attempts to contact participants, lost to follow-up will be determined after the date of the participant's projected last visit)
- Adverse event
- Pregnancy
- Protocol deviation (that results in discontinuation)
- Noncompliance to IP
- Physician (ie, investigator) decision
- Other

Safety follow-up for AEs should occur for all participants, for information on safety followup for withdrawn participants see Section 4.3.3.

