7.7 Breaking the Blind for Individual Participants

The blind may be broken if the health or safety of a participant is at risk and knowledge of the study arm may be beneficial to the medical management of the participant. The

PXVX0317 Vaccine EBSI-CV-317-004, Version 5.0 20 Mar 2023

pharmacist, investigator or other authorized individual may receive the allocation of an individual participant in the event that unblinding is required. In such an event, the sponsor must be notified.

If the investigator determines that knowledge of a participant's treatment assignment is urgently needed to guide treatment or ensure the participant's safety, the investigator may perform emergency unblinding via the RTSM system. The investigator may not delegate this responsibility. The investigator must attempt to notify the sponsor's MM prior to unblinding and must notify the MM within 24 hours after unblinding at the latest.

If a participant's study treatment assignment is unblinded for safety reasons, or if a participant becomes accidentally unblinded for any reason, the participant will be requested to remain in the study for safety follow-up.

The procedures to be followed in the event of an emergency unblinded for a medical emergency are outlined in the study pharmacy manual.

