8.3 Treatment Compliance

As the IP administration is a single 0.8 mL intramuscular injection performed by site personnel, measurements of treatment compliance are not applicable. A vaccine administration summary is provided and details listed.

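### Protocol 4.3.2 lets a dosed participant be withdrawn for noncompliance, and 4.3.3 plans no contact after the Early Withdrawal Visit, so new SAE, AESI and MAAE before Day 183 can be missed

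*Protocol*

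**What the plan says.** Protocol 4.3.2 gives a general permission: "The Investigator may withdraw a participant from further participation in the study, at their discretion, if medically necessary or for reasons of noncompliance". For noncompliance with the protocol the step is that "the issue should be discussed with the participant and, if not resolved, consideration given to withdrawing the participant". The same list of grounds applies to the sponsor. Consultation is advised but not required: "The investigator is encouraged to consult the sponsor prior to the withdrawal of any participant, except in the event of a medical emergency". None of this is limited to the period before the injection.

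Sections 4.3.1, 4.3.2 and 4.3.4 each say that safety follow-up for AEs should occur for all participants, and each refers to 4.3.3 for the details. There, outreach is to ensure that withdrawn participants "will complete all safety and available assessments for the Early Withdrawal Visit as outlined in this protocol". Further information on AEs already ongoing may be supplied as a follow-up report. Section 5.2.9 sets the content of that one visit according to when it falls.

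Elsewhere the commitment is wider. Section 3.3.12 states: "Serious adverse events, AESI, and MAAEs will be collected for all participants from Day 1 through Day 183 End of Study Visit". Section 7.5.2 says the study requires this monitoring up to the Day 183 visit. For a participant who has been unblinded, 7.7 says that "the participant will be requested to remain in the study for safety follow-up".

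**The concern.** In a trial with repeated dosing, withdrawal for noncompliance may at least end exposure. Here staff give a single injection on Day 1 (Protocol 1.3.4 and 5.4). For a dosed participant who has not asked to leave, withdrawal under 4.3.2 ends only observation.

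Incidence of AESI, MAAEs and SAEs through Day 183 is a primary safety endpoint (Protocol 8.3.1). The SAP reports counts and percentages in the safety population (SAP 5.3, 9.2.1 and 9.3) and plans no adjustment for follow-up time. A participant withdrawn early stays in the denominator, and an event after the last contact that nobody reports counts as no event.

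The Day 183 seroresponse difference is the second key secondary test (Protocol 8.6.2.5.2). Missing titers are excluded and not imputed (8.4), and dosed participants are not replaced (4.3.5). The documents do not say who would be noncompliant or why, so the resulting missingness may or may not be selective. Either way it is avoidable.

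**Working it through.** **The passages side by side**

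1. Who can be withdrawn: any participant with unresolved noncompliance, before or after dosing (4.3.2).
2. What is owed afterwards: AE safety follow-up for all (4.3.1, 4.3.2, 4.3.4), and SAE, AESI and MAAE collection for all through Day 183 (3.3.12, 7.5.2).
3. What is planned afterwards: one visit, then optional reports on ongoing AEs (4.3.3, 5.2.9). Section 7.5 follows known events until resolution, stabilization, or up to 30 days after the last study visit.
4. What is missing: no section says how a new SAE, AESI or MAAE would be found between the Early Withdrawal Visit and Day 183.
5. A comparison inside 4.3.2: loss to follow-up is determined only after the projected last visit. A participant who cannot be reached therefore stays open to about Day 183, while one who can be reached but is noncompliant may be closed out much earlier.

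**The plan's own figure**

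Protocol 8.1.3 gives 93.3% as the chance of seeing at least one AE of true frequency 0.1% among 2700 vaccinees. The formula is 1 − (1 − 0.001)^n. With n = 2700, 1 − 0.999^2700 = 0.9329, so the figure reproduces.

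**Effect of early loss**

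The documents give no withdrawal rate. I assume all-cause losses d of 2% to 10%, all at Day 22, with event risk spread evenly over the 182 days after dosing. The upper end borrows the plan's 10% non-evaluable rate, which was set for immunogenicity.

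- Follow-up lost per withdrawn participant: 182 − 21 = 161 days; 161/182 = 0.885.
- Effective n = 2700 × (1 − 0.885 d).
- d = 2%: n ≈ 2652; 1 − 0.999^2652 = 0.930.
- d = 10%: n ≈ 2461; 1 − 0.999^2461 = 0.915.
- Relative understatement of Day 183 incidence = 0.885 d: 1.8% at d = 2%, and about 9% at d = 10%.

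If withdrawn participants are instead assumed to contribute nothing at all, the figures are 92.9% (n = 2646) at 2% and 91.2% (n = 2430) at 10%.

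**Day 183 seroresponse**

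- Power for superiority (two-sided alpha 0.05, about 6:1 allocation) stays above 99.9% at every loss from 0% to 10%, assuming 5% response on placebo and 50% to 86% on vaccine.
- The estimate is more exposed than the test. Suppose 86% of observed vaccinees respond at Day 183 (an assumption). With 5% missing, the full-cohort rate lies between 0.86 × 0.95 = 81.7% and 81.7% + 5% = 86.7%. With 10% missing, it lies between 77.4% and 87.4%.

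**The case against.** The rule is permissive and guarded: discussion comes first, withdrawal is then only considered, and sponsor consultation is encouraged. The protocol repeats that AE follow-up should occur for all. Section 7.5.2 lists acceptable reasons to stop following ongoing SAEs, and noncompliance is not among them. Section 7.7 concerns unblinding, so its different treatment is a contrast and not a contradiction. All of this stands. It means that a reader who infers that follow-up ends at one visit, or that Day 183 safety data are simply lost, goes further than the text allows. It does not supply a contact at which a new event would be found.

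The Day 183 titer is also not left wholly without a sample. Withdrawal after Day 22 follows the Visit 8 schedule, which includes a serum draw. That draw is made at withdrawal, so it is not a true Day 183 value. SAP 5.5 includes all available data at time points other than Day 22 and does not say whether such an early sample may count as Day 183.

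Three stronger readings of the disposition records are tempting, and the documents support none of them:

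- That the loss would be invisible. SAP 7.1 tabulates participants still in the study at each scheduled visit and the reasons for not completing.
- That "Noncompliance to IP" is an impossible reason because the SAP says "measurements of treatment compliance are not applicable". Participants are enrolled at randomization, before dosing, and 4.3.5 provides for discontinuation between the two. The SAP sentence concerns measuring compliance only.
- That protocol noncompliance has no reason code. Section 4.3.4 lists protocol deviations that result in discontinuation, and 9.7 defines a deviation to include a participant's departure from protocol requirements. Consent withdrawal has no code of its own, but there is a category for other reasons.

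Finally, the 2% to 10% range is assumed all-cause loss. It includes consent withdrawal and loss to follow-up, which a change to 4.3.2 would not prevent. That stands too.

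**Conclusion.** The point holds in a limited form. The protocol permits withdrawal of a dosed participant for noncompliance when no treatment is left to stop. It promises SAE, AESI and MAAE collection through Day 183 but gives no means of finding new events after the Early Withdrawal Visit. Sections 4.3.2 and 4.3.3 need to be reconciled with 3.3.12 and 7.5.2.

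The size cannot be derived from the documents. The fall from 93.3% to between 93.0% and 91.5% rests on assumed all-cause losses, all at Day 22, and on evenly spread risk; the share due to noncompliance is unknown. The Day 183 superiority test is not at risk under the assumed response rates. The cost is avoidable, possibly selective missing data on a primary safety endpoint and on the Day 183 titer. That justifies a cheap improvement in wording. It does not show that the trial's conclusions are in doubt.

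**What to change.** - **Protocol 4.3.2:** state that after IP administration noncompliance with study procedures alone does not end participation, and that the remaining visits and contacts continue to be offered unless consent is withdrawn.
- **Protocol 4.3.3:** reconcile with 3.3.12 and 7.5.2. Ask dosed participants who stop attending whether they accept the already scheduled Day 29, Day 92 and Day 183 safety contacts, by telephone, and, if willing, the Day 183 sample.
- **Optional and minor, Protocol 4.3.4:** add a named reason for withdrawal of consent.

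The cost is protocol wording and a few more site calls to participants who may be hard to engage. The right to withdraw consent is unchanged.
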